10.0 Study Design / Methods

The mHealth SCD management intervention will be delivered via an app on both the caregiver and child mobile devices over a 12-week period. This multi-component, web-based app consists of 1.) continuous access to directed educational resources on the SCD process, treatment, home management strategies, symptom prevention and management strategies; 2.) a series of pages in the app that allow for tracking and monitoring symptoms; and 3.) child/caregiver – provider communication. The educational component is based on patient-centered materials that have been developed and tested by authoritative sources. In the app, educational materials are organized by user age (for individuals with SCD) or role for parents/caregivers. Citations are provided and links to the sources are included. The symptom tracking and monitoring component consists of a customizable avatar on which the user can record the location, severity, and characteristics of pain. Users can record other concurrent or associated symptoms (such as fatigue) and can view a graph

with the pain history. This portion of the app also includes a health history page on which users can document important clinical information, such as sickle cell type, last sickle cell crisis hospitalization, medications, and allergies. The child/caregiver – provider communication component consists of the ability for the child/caregiver to send a secure message to providers within the app to communicate pain and other symptoms. Providers will have the capability to securely send a reply within the app. In addition, children/caregivers can choose to receive a daily “support” message that will be automatically sent from a list of possible messages. All communication is encrypted and sent securely within the app via a portal. Two to three providers at the MUSC Sickle Cell Clinic will participate as the designated providers in the study.

To determine feasibility, we will apply the RE-AIM framework to assess the Reach, Efficacy, Adoption, Implementation, and Maintenance of the intervention with 30 children/caregiver dyads.¹⁸ The domains are further explicated in Table 1. The intervention will be loaded onto the child’s and caregiver’s tablet or smartphone (Apple or Android); participants without a device will be provided one for the duration of the study. The PI or PC will deliver detailed verbal instructions to the participants on the use of the device and the intervention. Participants will also receive written instructions and a contact number for technical assistance if needed. Baseline measures (Table 1) will be collected during the same meeting. Participants will retain the devices and will participate in the intervention over a 12 week-period. At the end of the 12-week period, the PI will conduct a post-intervention meeting with each individual caregiver and child participant during which post-intervention data collected. Caregivers will also be asked to return the mobile device at the end of the study. The PI will meet with the study provider weekly during the intervention.

Retention: To improve retention, IRB-approved personnel will contact enrolled participants at 3-week intervals between data collection points. The timeline for these points of contact are at the following weeks post baseline data collection: weeks 3, 9, 15, 18, and 21. The purpose is to maintain contact with enrolled participants, not data collection. Correspondence will be logged in REDCap. Contact will take place via text message, using the number(s) provided to study personnel upon enrollment. Examples of messages are provided in an uploaded attachment.

Post-intervention interviews. All 30 caregivers and their children will be asked if they would like to participate in the 3-month post-intervention key informant interviews with the PI to obtain more in-depth data on accessibility, usability, and adherence to intervention. However, only a subset of 15 dyads will be chosen to participate. Selection will be by computer at random. Both caregiver and child will have to agree to participate in the interview to be eligible for selection. Dyads have a 50-50 chance of being randomly selected. Semi-structured interviews will be conducted using a qualitative descriptive approach,¹⁷ will last approximately 45-60 minutes, and will be conducted according to an interview guide with open-ended questions and prompts. These interviews will be recorded for later nVivo qualitative data analysis. Reimbursement for dyads will be a \$50 gift card provided at each of the 4 data collection points, with dyads in key informant interviews receiving an additional \$40 gift card. All payments will be given to the caregiver. Selected caregivers will be given the option of having the interview conducted in-person in a private room at MUSC or by telephone in the comfort and safety of their own home.

Measures. Children (8-17 years) and Caregivers will complete age-appropriate self-report assessments at baseline, mid-intervention (6 weeks), post-intervention (12 weeks), and 3 months post-intervention as previously described. Self-report and proxy assessments will be collected during meetings between the PI or PC and the participant. Depending on participants’ preference and availability visit 2, 3 and 4 surveys will be completed either by phone or electronically via REDCap survey or by paper and pencil. All data will be recorded in REDCap by the PC.

11.0 Specimen Collection and Banking

Not applicable

12.0 Data Management

Sample size considerations

The purpose of this study is to establish feasibility of implementing the integrated intervention obtain estimates of variability for the primary outcome measures and obtain preliminary indicators of effectiveness of the intervention rather than to confirm or refute hypotheses. Therefore, sample size considerations focus on precision of estimates. For this feasibility study, we project that we will be able to recruit 30 child/caregiver dyads. With such a sample we will be able to estimate outcome proportions for feasibility measures including recruitment and drop-out with precision ± 0.11 to ± 0.16 for values of the true proportion ranging from 0.10 to 0.30 (or correspondingly, from 0.70 to 0.90). Assuming a drop-out rate of up to 30%, 95% confidence limits can be estimated for impact measures, such as change from pre-to-post in quality of life for child and caregiver with a precision ranging from ± 0.43 to ± 1.35 corresponding to estimated standard deviations for change in quality of life scores ranging from 0.5 to 5.0 SD units.

Demographic and clinical variables obtained at baseline will be described via measures of central tendency (mean, median), variability and frequency distributions as appropriate. Additionally, demographic and clinical characteristics for those who adhered to the study protocol (study completers) versus those who did not adhere (non-adherers and drop-outs) will be compared to better describe the population for this study. For continuous quality of life measures for the child and caregiver the difference between pre and post intervention measurements will be estimated via 95% confidence intervals. To assess preliminary intervention effects, we will conduct repeated measures ANCOVA with symptom (pain) severity and type obtained daily as dependent variable in individual models adjusting for “dose” defined as number of times education module was accessed and total time spent in education modules.

Post-intervention qualitative analyses (Aim 2): Data collected from post-intervention key informant interviews will be analyzed using directed content analysis¹⁹ and nVivo qualitative data analysis software version 11.²⁰ Consistent with the directed content analysis approach, initial coding categories are identified according to the guiding theoretical model, and for this study, will reflect the RE-AIM domains.

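### The stated precision for pre-to-post quality-of-life change (± 0.43 to ± 1.35) does not follow from SDs of change of 0.5 to 5.0 with 30 dyads and 30% drop-out

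*Combined protocol and SAP*

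**What the plan says.** The sample size text in Section 12.0 (Data Management) rests on precision rather than power. It starts from a recruitment projection: "we project that we will be able to recruit 30 child/caregiver dyads". For the outcomes that serve the secondary aim it continues: "Assuming a drop-out rate of up to 30%, 95% confidence limits can be estimated for impact measures", the example being "change from pre-to-post in quality of life for child and caregiver". The precision is then given as "precision ranging from ± 0.43 to ± 1.35 corresponding to estimated standard deviations for change in quality of life scores ranging from 0.5 to 5.0", and the sentence ends by calling these values SD units. The planned analysis matches this, in that "the difference between pre and post intervention measurements will be estimated via 95% confidence intervals".

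The same figures appear in Section 12.0 of the 8-17 years protocol and of the 0-7 years protocol. Neither gives a formula, a pre-post correlation or a comparison group. The same paragraph also gives a precision for the feasibility proportions: "precision ± 0.11 to ± 0.16 for values of the true proportion ranging from 0.10 to 0.30".

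**The concern.** At a fixed number of pairs and a fixed confidence level, the half-width of the interval for a mean change is a constant times the SD of change. The stated SDs run from 0.5 to 5.0, a factor of 10. The stated half-widths run from 0.43 to 1.35, a factor of about 3.14. No single sample size can produce both ends.

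The study tests no hypothesis, so precision is its only quantitative sample size argument, and this sentence is the only precision figure for the secondary aim. A reader who uses it to judge what the pre-post intervals can show, or to plan the next trial, would expect much narrower intervals at the large-SD end than 30 dyads can deliver.

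**Working it through.** **Inputs, all from Section 12.0.** 30 dyads; drop-out up to 30%, so 30 × 0.70 = 21 completed pairs in the worst case and 30 in the best; 95% two-sided intervals; one group, within-participant change; SD of change 0.5 to 5.0.

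**Cross-check on the same paragraph.** The normal-approximation half-width for a proportion, 1.96 × √(p(1 − p)/30), gives 0.107 at p = 0.10 and 0.164 at p = 0.30. These are the stated ± 0.11 and ± 0.16, so the feasibility figures are correct.

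**Half-width for a mean paired change:** c × SD/√n, with c = 1.96 (normal) or the t quantile on n − 1 df (2.086 for 20 df).

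| Completed pairs | Method | SD 0.5 | SD 5.0 |
|---|---|---|---|
| 21 | t | 2.086 × 0.5/√21 = 0.228 | 2.086 × 5.0/√21 = 2.276 |
| 21 | normal | 0.214 | 2.138 |
| 30 (no drop-out) | t | 0.187 | 1.867 |
| 30 (no drop-out) | normal | 0.179 | 1.789 |
| Stated | – | 0.43 | 1.35 |

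**Ratio test, which needs no assumption about n.** Stated: 1.35/0.43 = 3.14. Allowing for rounding, it lies between 1.345/0.435 = 3.09 and 1.355/0.425 = 3.19. Required: 5.0/0.5 = 10. Choosing t or normal, another confidence level, full width instead of half-width, a factor √2 or a common pre-post correlation multiplies both ends by the same amount and leaves the ratio at 10. So does any rescaling of the units.

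**Could varying drop-out explain it?** Solving n = (1.96 × SD/half-width)² gives (1.96 × 0.5/0.43)² ≈ 5.2 pairs for the lower end and (1.96 × 5.0/1.35)² ≈ 52.7 pairs for the upper end. Neither lies between 21 and 30. With t, ± 1.35 at SD 5.0 needs about 56 completed pairs.

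**Where the stated values may come from.** With v = 0.5 and 5.0 entered as variances and doubled:

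- 1.96 × √(2 × 0.5/21) = 0.428
- 1.96 × √(2 × 5.0/21) = 1.353

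Both stated values are recovered to two decimals with n = 21 and 95% confidence. The ratio agrees too, since √10 = 3.16. The doubling is what one would use for two independent groups, or for one group whose pre and post scores are uncorrelated. If 0.5 and 5.0 were variances of the change itself, no doubling would apply and the half-widths would be 1.96 × √(0.5/21) = 0.302 and 1.96 × √(5.0/21) = 0.956, which are not the stated figures either.

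**What the stated values imply.** Half-widths of 0.43 and 1.35 with 21 pairs correspond to SDs of change of 1.01 and 3.16 (normal) or 0.94 and 2.97 (t).

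**The case against.** The inconsistency itself cannot be argued away, but its weight and its direction can.

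- **N does not depend on it.** The 30 dyads are a projection of what can be recruited, not the solution of a precision equation. The primary aim is feasibility, and its precision figures are right. No decision rule uses ± 0.43 or ± 1.35, and the final intervals will come from the observed data. All of this stands and keeps the practical consequence modest.
- **The inputs, not the outputs, may be mislabelled.** If 0.5 and 5.0 were meant as variances at each time point with zero pre-post correlation, the stated half-widths would follow, and positive correlation would make the real intervals narrower. This is possible, but it is not what the text says: it calls them standard deviations, and of change. The sentence needs correcting on this reading too.
- **SD units have no clear scale here.** An SD expressed in SD units is ambiguous. That is fair and should be resolved, but no change of scale turns a ten-fold range into a three-fold one.
- **The 69% is the least favourable comparison.** It uses t and the full 30% drop-out. With the normal approximation it is 58%. With no drop-out it is 33% (1.789/1.35) to 38% (1.867/1.35). The lower end, moreover, errs on the cautious side. These qualifications are correct, and in none of these cases is ± 1.35 attained at SD 5.0.

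**Conclusion.** The concern holds: the sentence is wrong at both ends, in opposite directions. Taking the inputs as written (paired change, SD of change 0.5 to 5.0, 21 completed pairs, 95% confidence), the half-widths are ± 0.23 to ± 2.28 with t. The stated lower figure is about twice the correct one (0.43/0.228 = 1.9). The stated upper figure is about 41% too small (1 − 1.35/2.276), or 37% with the normal approximation.

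That the two figures cannot both be right rests on proportionality alone. The size of each error rests on the inputs being SDs of change, as the text states. The variance explanation fits exactly but remains an inference, because no formula is given. The figure is part of the stated sample size rationale and should be corrected, although neither the number of dyads nor the analysis has to change.

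**What to change.** In Section 12.0 of both protocols:

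1. Replace the stated range by ± 0.23 to ± 2.28 for SDs of change of 0.5 to 5.0, and give the basis: paired change, 21 completed pairs, t with 20 df. A scale-free alternative is ± 0.46 SD of change (2.086/√21 = 0.455).
2. Say whether 0.5 to 5.0 are score points or multiples of a named SD.
3. If other inputs were intended, such as per-occasion variances, state them with the formula and the assumed pre-post correlation, and recompute the half-widths for the paired, single-group design.

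The cost is protocol wording only. The upper figure becomes less favourable. No more participants, visits or analyses are needed.

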Demographics/clinical characteristics	Age, child age, health history, race/ethnicity, medications, health care utilization, rural/urban residence, insurance, caregiver demographics, family characteristics	Caregiver interview; baseline
Reach: Sample Recruitment	Monitoring of sample representativeness; types of recruitment activities; rates of recruitment; % eligible, consented, provided with informational session	Recruitment tracking forms; quality checks by PI; weekly meetings with mentor, clinic staff, and research team
Efficacy: Child (by proxy): Pain Fatigue Quality of life Caregiver: Fatigue Emotional distress: anxiety Emotional distress: depressive symptoms Measures of self-management behaviors: Monitoring and tracking symptoms Attending clinic appointments Administering home medications and treatments	PROMIS Parent Proxy: Pain Interference* ^{21,22} (age 5 and older) Self-efficacy SEMCD-6 PedsQL with Sickle Cell Disease Module (proxy = 0.97) ²³ (age 2 and older) PedsQL Multidimensional Fatigue Scale in Sickle Cell Disease (proxy = 0.95) ²⁴ (age 2 and older), PROMIS Fatigue SF, Depression SF (>0.9) ²⁵ PROMIS Emotional Distress: Anxiety (0.97) ²⁶ PROMIS Emotional Distress: Depressive symptoms SF (0.97) ²⁷ Daily pain severity rating; daily pain type rating # days recorded symptoms; # days and types of recorded treatments; # scheduled clinic appointments attended; # days daily mediation administered; # days PRN medications administered	Review and content analysis of transcriptions of text messages; review and content analysis of recorded teleconferences; tracking forms; fidelity checklist; transmissions from web-based application to nurse; post-intervention interviews; weekly meeting with mentor, clinic staff, and research team; baseline, mid-intervention, post-intervention, 3-months post-intervention

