5.0 Inclusion and Exclusion Criteria/ Study Population

- Eligible caregiver/child dyads will be identified through the staff at the MUSC Pediatric Sickle Cell Clinic. After receiving permission to approach, PI or PC will

screen the potential participants against the inclusion and exclusion criteria. Screening will be documented in REDCap.

Inclusion Criteria

- Children ages 0 – 7 years and parent or primary caregiver 18 years of age or older
- Child with sickle cell disease, as reported by clinician at the MUSC Pediatric Sickle Cell Clinic

Exclusion Criteria

- Parent/caregiver with cognitive disability or delay that precludes ability to participate
- Lack of access to Wi-Fi

Inclusion of Women and Minorities

Both women and minorities will be included in the proposed study. Women are more often than men reported to be the primary caregiver of children with chronic conditions and approximately 66% of caregivers of adults with chronic illness are women. Therefore, it is anticipated that more women will be recruited as participants than men. In addition, SCD occurs almost exclusively in African Americans; therefore, it is anticipated that all or nearly all of the caregiver participants will be African American.

Inclusion of Children

Children ages 0-7 years will be included as part of the child/caregiver dyad. Proxy data will be collected on children younger than 5 years, and older children (ages 5-7 years) without developmental delay will be invited to complete surveys and participate in key informant interviews with the caregiver.

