Reimbursement for dyads will be a \$50 gift card provided at each of the 4 data collection points, with dyads in key informant interviews receiving an additional \$40 gift card. All payments will be given to the caregiver.

Measures. Older children (5-7 years) and their caregivers will complete age-appropriate self-report and proxy assessments at baseline, mid-intervention (6 weeks), post-intervention (12 weeks), and 3 months post-intervention as previously described. Self-report and proxy assessments will be collected during meetings between the PI or PC and the participant. Depending on participants' preference and availability visit 2, 3 and 4 surveys will be completed either by phone or electronically via REDCap survey or by paper and pencil. All data will be recorded in REDCap by the PC.

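### Quality-of-life change is planned only as a pre/post difference, with up to 30% drop-out assumed and no stated quantitative analysis of the 6-week and 3-month scores

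*Combined protocol and SAP*

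**What the plan says.** The document holds two protocols, for ages 8-17 and ages 0-7, with the same analysis text in Section 12.0.

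- **Analysis.** For continuous quality-of-life measures of child and caregiver, "the difference between pre and post intervention measurements will be estimated via 95% confidence intervals". No analysis set and no missing-data method is named.
- **Drop-out.** The sample-size paragraph reads "Assuming a drop-out rate of up to 30%, 95% confidence limits can be estimated for impact measures" and gives a precision of ±0.43 to ±1.35.
- **Visits.** Section 10.0 schedules "age-appropriate self-report assessments at baseline, mid-intervention (6 weeks), post-intervention (12 weeks), and 3 months post-intervention" (ages 8-17) and "age-appropriate self-report and proxy assessments at baseline, mid-intervention (6 weeks), post-intervention (12 weeks), and 3 months post-intervention" (ages 5-7 and caregivers). The Efficacy row of the Section 3.0 measures table, which holds the quality-of-life and PROMIS scales, lists "baseline, mid-intervention, post-intervention, 3-months post-intervention".
- **Other analyses.** The one repeated-measures model takes daily pain severity and type as outcomes. Drop-outs appear only in a comparison of demographic and clinical characteristics, in which completers and "those who did not adhere (non-adherers and drop-outs) will be compared to better describe the population for this study". The interviews are analysed qualitatively.
- **Purpose.** The aim is to obtain estimates of variability and preliminary indicators of effectiveness, "rather than to confirm or refute hypotheses".

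**The concern.** A within-family difference needs both scores. With no other rule stated, a family without the later score contributes nothing to the estimate, even if it gave a baseline and a 6-week score. If leaving is related to how quality of life is changing, the mean and SD of change describe only the families who stayed. The direction is unknown. Loss of worsening families would make the result look too good, and loss of improving families would do the reverse.

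Two outputs that the study exists to produce are affected: the preliminary change and its variability, and any view of whether a change persists. The 3-month visit falls at about week 24 (12 weeks plus 3 months). Families are asked and paid for that survey, yet no estimate from it is planned.

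**Working it through.** **1. The plan's own precision.** Inputs from Section 12.0: 30 dyads and up to 30% drop-out, so 30 × 0.7 = 21.
- As labelled, with an SD of change of 0.5 and 5.0: 1.96 × 0.5/√21 = 0.21 and 1.96 × 5.0/√21 = 2.14. These are not the stated figures.
- With 0.5 and 5.0 read as variances of a single score, and pre and post uncorrelated: 1.96 × √(2 × 0.5/21) = 0.428 and 1.96 × √(2 × 5.0/21) = 1.352. These match ±0.43 and ±1.35.

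The mislabelled SDs are a separate matter. What counts here is that the stated precision fits n = 21, which supports the complete-pair reading.

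**2. Size of the bias in general.** If the mean change of drop-outs differs from that of completers by d, the completer mean is off by 0.3 × d at 30% loss. That is 0.075, 0.15 and 0.30 SD for d = 0.25, 0.5 and 1.0.

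**3. Bias under a drop-out model.** The documents give no correlations or slopes, so all of them are assumptions. Units are the SD of one visit, with no true change. Drop-out follows logit P = a − slope × (6-week change), with slopes from 0.25 to 3 and 1,000,000 draws per correlation set (Monte Carlo offset up to 0.003). Reversing the slope reverses the sign. The half-width is t × √(2 − 2r)/√n, where r is the correlation between weeks 0 and 12. At n = 21 and 30% loss:

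| Correlations 0-6, 6-12, 0-12 weeks | 95% half-width | Completer bias, slope 0.25 to 3 | Completer bias, slope 1 | Left by unstructured model, half leave before week 6 (slope 1) | Left, all leave before week 6 (slope 1) |
|---|---|---|---|---|---|
| 0.7, 0.7, 0.5 | 0.455 | 0.04 to 0.26 | 0.136 | 0.040 (about 28%) | 0.097 (about 71%) |
| 0.5, 0.5, 0.3 | 0.539 | 0.05 to 0.30 | 0.178 | 0.039 (22%) | 0.094 (53%) |
| 0.8, 0.8, 0.7 | 0.353 | 0.02 to 0.17 | 0.083 | 0.028 (34%) | 0.067 (81%) |

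The percentages in the first row allow for the Monte Carlo offset. Across slopes, about 20% to 36% remains if half leave before week 6, and about 50% to 82% if all do. If every drop-out first gave a 6-week score, the model leaves essentially nothing.

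With less loss, the first set gives 0.02 to 0.18 at 20% (n = 24, half-width 0.42) and 0.01 to 0.10 at 10% (n = 27, half-width 0.40).

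**4. If drop-out depends on the unseen 12-week change.** For the first set at 30% loss and no early loss, completer bias is 0.074 to 0.429 and the model leaves 0.039 to 0.269 (0.039/0.074 = 53%; 0.269/0.429 = 63%). Across the three sets about 52% to 68% remains with no early loss, and up to about 89% if all leave before week 6.

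**5. Precision (n = 30, nine lost).** Standard error of the 12-week change, complete pairs against the unstructured model: 0.2147 and 0.2018 with four visits (6% lower); 0.2184 and 0.2122 if all nine leave before week 6 (3% lower); 0.2174 and 0.2031 with three visits (7% lower).

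**6. Choice of covariance.** In 300 simulated studies each, REML with unstructured covariance converged every time at n = 30 (nine lost) and at n = 11 (three lost). Mean standard error over empirical SD was 0.95 at both sizes. For heterogeneous compound symmetry it was 0.87 and 0.91, and that structure left 28% to 40% of the bias even with no early loss. It therefore serves only as a fallback. Kenward-Roger coverage was not simulated.

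**The case against.** The primary aim is feasibility, drop-out is itself a feasibility result, and 30% is a ceiling. Both protocols work to limit loss with flexible survey modes, $50 at each of four data collection points, retention texts and weekly contact. No decision rule uses the quality-of-life estimate, and every bias figure rests on assumed inputs. The top of the range needs slope 3, an odds ratio of about 20 per SD (e³). For the first correlation set at 30% loss, coverage of the planned interval stays near 94.7% at slope 0.25 and about 91% at slope 1. Only slope 3 brings it to about 80%. All of this stands and sets the weight of the point. None of it says how missing scores are analysed.

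Three stronger readings are tempting, and the documents support none of them.
- **The plan restricts the analysis to completers.** No sentence says so. It is an inference from a paired difference, the lack of a missing-data method and the match to n = 21.
- **The reported change will be wrong by up to 0.30 SD.** The documents give no sign that loss is related to change.
- **A mixed model would cure attrition.** Steps 3 and 4 show that it does so only for loss explained by scores already given.

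Section 12.0 does not tie the later measurement to week 12. Section 10.0 labels week 12 as post-intervention, so that is the natural reading. If the 3-month visit were meant instead, the 6-week and 12-week scores would be the ones with no stated analysis.

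**Conclusion.** The omission is real in both protocols: one pre/post difference, up to 30% drop-out assumed, no missing-data method, and two of four scheduled visits without a stated quantitative analysis. At 30% loss that depends on 6-week change, the completer bias is about 0.02 to 0.30 SD, below the half-width (0.35 to 0.54) in every case examined and large only at steep slopes. These sizes rest on assumed correlations, slopes and a logistic drop-out model.

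The consequence is confined to the secondary-aim change and SD carried forward, and to persistence at about week 24. Feasibility results are not touched. No model makes a change seen without a control group attributable to the app. This is a cheap improvement of low to moderate priority.

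**What to change.** In Section 12.0 of both protocols, replace the pre/post sentence with:

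> For each continuous quality-of-life scale and respondent, change is estimated by a linear mixed model (REML, Kenward-Roger df) with visit (0, 6, 12 and 24 weeks) as a categorical effect and unstructured covariance, using every participant with any score. Heterogeneous compound symmetry is used only if the unstructured model does not converge. The 12-week and 24-week changes are reported with 95% CIs, and the complete-pair pre/post difference is reported beside them as a sensitivity analysis.

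Apply the same model to the PROMIS scales in the Efficacy row, which share the visit schedule.

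In the 0-7 protocol, keep child self-report descriptive. Only "older children (ages 5-7 years) without developmental delay will be invited to complete surveys", which is about 30 × 3/8 = 11 children if ages are uniform (an assumption).

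A shift analysis of imputed scores is not requested. It would need a stated imputation model and reference SD. Section 14.0 needs no change.

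**Cost.** A little more analysis of data already scheduled. Payment at all four points is already planned, so there is no added participant cost, and the planned pre/post difference is kept. The gain in precision is small. The model helps less for families lost before week 6, and it does not protect against loss that depends on unobserved scores.

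### Repeated measures ANCOVA on up to 84 daily pain ratings from at most 30 children per protocol is planned with no time term, covariance structure or rule for unrecorded days, and its classical form does not suit such data

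*Combined protocol and SAP*

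**What the plan says.** The document holds two protocols, one for ages 8-17 and one for ages 0-7. Their Section 12.0 texts on this point are the same: "we will conduct repeated measures ANCOVA with symptom (pain) severity and type obtained daily as dependent variable in individual models". The stated adjustment is for a dose "defined as number of times education module was accessed and total time spent in education modules". No other regressor is named.

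The length of the daily series comes from Section 10.0. In the 8-17 protocol, "The mHealth SCD management intervention will be delivered via an app on both the caregiver and child mobile devices over a 12-week period", and "Participants will retain the devices and will participate in the intervention over a 12 week-period"; the 0-7 protocol gives the same 12 weeks on the caregiver's device. The size of the sample comes from Section 12.0: "we project that we will be able to recruit 30 child/caregiver dyads".

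Both protocols expect incomplete series. The measures table in Section 3.0 lists "Daily pain severity rating; daily pain type rating # days recorded symptoms", and the Adoption row counts days recorded again as adherence. Section 12.0 adds: "Assuming a drop-out rate of up to 30%, 95% confidence limits can be estimated for impact measures".

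Neither protocol says how time enters the model, what correlation between days is assumed, whether a sphericity correction is applied, or what happens to days without a rating.

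**The concern.** Repeated measures ANCOVA, in its classical form, was built for a few occasions and complete data. Here there may be nearly three times as many occasions as children, and logging depends on the user. Under that form the multivariate test does not exist and incomplete children are removed. The univariate version keeps a simple error term only by treating every pair of days as equally correlated, although neighbouring days of pain are likely to be more alike and children may follow different courses.

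This is the only regression-type model in the plan, and its stated job is to look for preliminary intervention effects. Section 12.0 also says that the study is sized for precision and is meant to yield estimates of variability. A standard error for change over the 12 weeks that is too small, or an estimate from a small subset of diligent loggers, would undermine that purpose. The unstated choices decide which result is obtained.

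**Working it through.** **Plan's own figures.** Section 12.0 gives no precision, power or error figure for this model, so there is none to reproduce. The section's precision for proportions, "with precision ± 0.11 to ± 0.16 for values of the true proportion ranging from 0.10 to 0.30", does reproduce with 30 dyads: 1.96·√(0.10·0.90/30) = 0.107 and 1.96·√(0.30·0.70/30) = 0.164. The working sample is therefore 30 per protocol, or 30 × 0.70 = 21 after the assumed drop-out.

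**Occasions.** 12 weeks × 7 = 84 days (derived; the documents do not print 84).

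**Multivariate form.** It needs 84 − 1 = 83 within-child contrasts. Thirty children give at most 29 error degrees of freedom, so the error matrix is singular even with perfect data. An unstructured covariance would have 84·85/2 = 3,570 parameters.

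**Complete series.** Drop-out alone could remove 9 of 30. For missed days, let each day be logged with probability q, independently and at the same rate for all children (assumed). Then P(complete) = q^84.

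| q | P(complete) | Expected complete, of 30 |
|---|---|---|
| 0.99 | 0.430 | 12.9 |
| 0.98 | 0.183 | 5.5 |
| 0.95 | 0.013 | 0.4 |
| 0.90 | 0.0001 | 0.004 |

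If children differ in their logging rate, more are complete. With a mean of 0.95 and beta-distributed child rates (parameters summing to 50, 20, 10 or 5; assumed), 8%, 18%, 32% or 47% are complete, which is 2.4 to 14.2 of 30.

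**Error of a linear time trend.** Simulation with 2,000 runs per setting, 84 complete days, no true trend, a random intercept with 40% of the variance, and first-order autoregressive residuals with correlation ρ (all assumed). Entries are rejection rates at a nominal 5%. The standard-error ratio is the child-level standard error divided by the pooled equal-correlation one.

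| ρ | SE ratio (n = 30) | Pooled trend test, n = 30 | Pooled trend test, n = 21 | Child-level slopes, n = 30 | Child-level slopes, n = 21 |
|---|---|---|---|---|---|
| 0 | 1.00 | 4.8% | 5.0% | 4.6% | 4.8% |
| 0.3 | 1.34 | 13.6% | 14.2% | 4.6% | 5.6% |
| 0.5 | 1.69 | 26.2% | 25.4% | 5.6% | 4.5% |
| 0.7 | 2.31 | 40.2% | 41.6% | 4.2% | 5.1% |

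A rough check is 2Φ(−1.96/ratio): ratios of 1.34, 1.69 and 2.31 give 14%, 25% and 40%.

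**Independent days, child-specific slopes.** Let the slope SD be 0.5 residual SD over the 12 weeks (assumed). With Sxx = 84·(84² − 1)/12 = 49,385, the true variance of a child's slope exceeds the residual part by a factor 1 + (0.5/83)²·49,385 = 2.79. The pooled residual variance rises only to 1 + 0.25·49,385/83³ = 1.02. The ratio is √(2.79/1.02) = 1.65, so the rejection rate is about 2Φ(−1.96/1.65) = 0.235; simulation at n = 21 gives 23%. A larger assumed slope SD (0.5/√0.6 = 0.65 residual SD, n = 30) gives 32.8%. Child-level slopes stay near 5% in both.

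**Overall day effect.** The uncorrected F test over all days is less affected: 6.2%, 9.2% and 14.2% at ρ = 0.3, 0.5 and 0.7 (n = 30). With the Greenhouse-Geisser correction it rejects only 0% to 1.2%.

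**The case against.** The strongest reply is that the documents do not commit to the classical form. Repeated measures ANCOVA is also used as a label for likelihood-based mixed models, which keep incomplete series and allow serial correlation. Nothing in either protocol specifies listwise deletion or equal correlation. This stands: a reader might infer that the plan must either discard incomplete children or assume equal correlation, and the text does not support that.

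Second, no time trend is named. The trend is inferred because every dyad receives the app, no comparator is described, and education use appears only as an adjustment. Even the classical analysis can test a linear contrast against its own child-by-contrast error, which holds about 5%. So a reader who concludes that the trend errors are wrong would be describing one variant of a test that the plan does not mention. This also stands.

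Third, neither a daily completion rate nor a day-to-day correlation is given. A claim that almost no children would remain depends on independent misses at a common rate.

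Fourth, Section 12.0 says that the study is not meant to confirm or refute hypotheses, and no significance level is set. That limits the consequence. It does not remove it, because a plan aimed at precision still needs a standard error that can be interpreted, and the silence on time, covariance and missing days remains.

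**Conclusion.** The concern holds as a gap in specification with a real downside, and the change is worth making. From the documents alone: up to 84 occasions, at most 30 children per protocol, incomplete series expected, and no time term, covariance structure or missing-day rule. It follows without further assumption that the classical multivariate version cannot be fitted, and that the classical form drops any child with a missing day.

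The sizes rest on assumptions. Complete series range from 13 of 30 at 99% independent daily logging to 0.4 of 30 at 95%, with more if logging varies by child. A pooled equal-correlation trend test gives about 15%, 25% and 40% false positives at ρ = 0.3, 0.5 and 0.7, and about 23% with independent days and the assumed child slopes. With ρ = 0 and common slopes there is no inflation.

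The documents do not show that the eventual analysis will be invalid. The feasibility proportions and the pre-post confidence intervals in Section 12.0 are untouched.

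**What to change.** In Section 12.0 of both protocols, replace the named method for daily pain severity with a linear mixed model on all available days. State:

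- an explicit time term (for example day since start, linear) as the quantity of interest;
- the two planned education-dose covariates;
- a random intercept and slope per child;
- serially correlated residuals, for example AR(1) indexed by calendar day so that gaps are handled;
- REML with small-sample degrees of freedom;
- a fallback if the model does not converge: weekly means with the same random effects, or child-level slopes.

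State that unrecorded days are assumed missing at random given the recorded data. Add one sensitivity analysis for departures from this, since users may log more on painful days; repeating the model with unrecorded days set to a low pain value would be one way.

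Give pain type its own model, suited to the scale on which it is recorded, because a linear model for severity does not cover it.

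The cost is a few sentences in each protocol and modest extra analysis time in standard software. No new data are needed.
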